Compassion, empathy, mindfulness, and social connectedness: As a feasibility study, we will use a larger array of measures than we anticipate employing in a subsequent VA Merit-supported RCT. Although we have prior experience with each of these measures in other contexts, their use in this feasibility study will enable us to more comprehensively identify those with most potential and which are most appropriate for this population. Measures will include: Self-Compassion Scale – Short Form, Toronto Empathy Questionnaire, Cognitive and Affective Mindfulness Scale – Revised, Social Connectedness Scale - Revised and the UCLA Loneliness Scale - Third Edition.

Well-being/Quality of Life: Physical and mental composite scores from the 12-item Short Form Health Survey (SF-12) and Satisfaction with Life Scale.

General positive psychological factors: 10-item version of the Connor-Davidson Resilience Scale , Life Orientation Test – Revised (a measure of optimism) , San Diego Wisdom Scale (SD-WISE)) and Center for Epidemiological Studies – Depression Scale (CES-D; happiness factor).

Biomarkers: At the baseline and final visits, approximately 15 mL (2-3 teaspoons) of blood will be drawn from each participant by the VA Clinical Laboratory via standard blood draw. Three inflammatory markers will be assayed: high sensitivity C-reactive protein (hs-CRP), interleukin-6 (IL-6), and tumor necrosis factor-alpha (TNF-). Assays will be conducted using standardized methods through the VASDHS 6th floor research laboratory of Co-I [name].

Additional final visit measures: Participants will complete the modified Differential Emotions Scale (mDES) (Fredrickson et al., 2003) at each weekly session to assess changes in positive emotion during the course

of treatment. Credibility of the interventions will be assessed at the final visit with a 3-item measure adapted from Borkovec & Nau (1972) and the Client Satisfaction Questionnaire (Attkisson & Greenfield, 1994) as well as via post-intervention interviews.

Analytic plan:

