The associations between patient characteristics and other clinically important baseline variables with the enrollment, completion and adherence will be assessed using univariate tests (Wilcoxon rank sum test, Kruskal-Wallis test, Fisher's exact test, or Spearman correlation coefficient).

Does CM show promise for improving well-being, symptom severity, and/or positive psychological factors relevant to successful aging? We will evaluate the improvement in depression and anxiety (BSI), social connection (SCS-R), satisfaction with life (SWLS) and positive emotions (mDES) from baseline to post-intervention using a linear random effect model and time will be included as a main effect in the model. The random effects model is suitable for examining changes in outcomes in longitudinal studies. It will include all available data, minimizing the effects of missing data on the analyses.

We will also examine the mean (and SD) change scores for each inflammatory biomarker (hs-CRP, IL-6, and TNF-), as well as the association of these changes with practice time.

Sample size assessment:

The sample size was determined based on practical consideration. Since this is a feasibility study, the goal is to examine the effect size such that it can guide future studies. We plan to enroll a total of approximately 24 to 30 participants for the CM groups (3 groups, 8-10 per group) as well as 10 participants for the healthy aging group. Sample size analyses were focused on the CM group, and performed using statistical package R.

A two-sided type I error of 0.05 was assumed.

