*Virtual Research Sessions and Cisco WebEx: During the COVID-19 administrative hold, ORD-funded grants are not permitted to have in-person study visits (including blood draw) for non-clinically critical research assessments. Therefore, we will conduct Compassion Meditation (CM) group therapy sessions and individual pre- and post-intervention sessions using the VA-approved telehealth technology, "Cisco WebEx." We will use Cisco WebEx to conduct the remaining CM group therapy sessions and post-intervention sessions with the first participant cohort as well as to conduct virtual research sessions with future cohorts that are enrolled during the COVID-19 administrative hold. We will use Cisco WebEx to create digital recordings of the group therapy sessions for training and supervision of the study therapist. The recordings will be stored as digital files on the secure VASDHS R-drive network in the PI's R Drive folder (R: [name]) and will only be accessible to VA IRB-approved study staff. The use of Cisco WebEx to conduct virtual research visits is explained to participants in the new Verbal ICF/Script (see attached "Uploaded Documents").

Cisco WebEx is a subscription-based managed service that connects VA to a fully featured FedRAMP Cloud solution. It offers resources for conferencing, webinars, training, collaboration and more. VA staff can schedule and host conferences with both internal VA users and external participants. It is a PIV-enabled and integrates Single Sign-On (SSO). Only staff that need to host or scheduled a meeting need an account.

All scheduled WebEx meeting links will be emailed to each participant securely via Azure encrypted email one day prior to the scheduled meeting day.

Additional information about Cisco WebEx privacy and security features is included in Sections 9.11 and 27.5.

Prior to the first virtual group session, a member of the study team will assist each participant in using Cisco WebEx to ensure participants are comfortable using the program during the virtual research visits. The study therapist, [name], will also review proper participant etiquette and expectations for the new virtual format. [name] will review the previous 3 therapy sessions materials and ensure the participants are comfortable moving forward in the remaining virtual therapy sessions. During the virtual group sessions, a member of the study team will be available to assist participants with any difficulties they may have.

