We will also mail a packet to each participant, which will include information and instructions for virtual research visits, instructions for using Cisco WebEx, and printouts of the weekly study questionnaires. Participants will be instructed NOT write their name, date, initials, or any other personally identifiable information on any of these documents. Prior to each of the group training sessions, a member of our study team will meet one-on-one with each participant via Cisco WebEx to review and collect participants' responses to the questionnaires.

*Blood-Based Inflammatory Biomarkers: The collection of blood-based inflammatory biomarkers, which were included for exploratory purposes, will not be collected during the COVID-19 administrative hold.

*New "Uploaded Documents" for use during COVID-19 Administrative Hold:

- $1. \ \ \ Verbal\ ICF/Script\ for\ virtual\ study\ sessions\ with\ the\ current\ participant\ group$
- 2. General instruction letter for virtual research visits
- 3. "Joining a WebEx Meeting" instruction letter
- 4. "Participating in a WebEx Meeting" instruction letter
- 5. CAIR Pandemic Questionnaire**
- 6. 4-item Duke Social Support Index**
- 7. 6-item De Jong Gierveld Loneliness Scale**

**The CAIR Pandemic Questionnaire was developed by the VA Center of Excellence for Stress and Mental Health (CESAMH). The nature of our study population (ages 55 years and above, identified in VA primary care) includes risk factors for worse reactions to infection from this virus. In addition to the profound medical challenges inherent to the COVID-19 pandemic, the necessary safety and prevention social distancing requirements are likely to affect social interactions, relationships, and loneliness. Some aspects of these changes may be positive for some persons,

and negative for others. The focus of the study on anxiety and depressive symptoms in terms of compassion, self-compassion, and connectedness, also has direct relevance to these secondary effects of the pandemic. Thus, in order to collect systematic data on the effects of the pandemic on our participants in these aspects, we will administer the CAIR Pandemic Questionnaire, 4-item Duke Social Support Index, and 6-item De Jong Gierveld Loneliness Scale.

Post-Intervention and Participant Withdrawal Data**

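### In the first CM class the way the weekly mDES is collected changes after session 3, and the time-only model would read any resulting shift as change over time

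*Combined protocol and SAP*

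**What the plan says.** All the relevant text is in Section 9.

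- **Additional final visit measures.** The mDES is completed "at each weekly session to assess changes in positive emotion during the course" of treatment. Nothing is said about whether the form is filled in before, during or after the group, or how staff handle it. The mDES is not in the list of baseline and post-intervention measures.
- **Temporary COVID-19 Updates.** "We will use Cisco WebEx to conduct the remaining CM group therapy sessions and post-intervention sessions with the first participant cohort". The study therapist "will review the previous 3 therapy sessions materials and ensure the participants are comfortable moving forward in the remaining virtual therapy sessions". Participants are mailed "printouts of the weekly study questionnaires". Then: "Prior to each of the group training sessions, a member of our study team will meet one-on-one with each participant via Cisco WebEx". The stated purpose of this individual meeting is "to review and collect participants' responses to the questionnaires".
- **Analytic plan.** Change from baseline to post-intervention in the BSI, SCS-R, SWLS and mDES is evaluated "using a linear random effect model and time will be included as a main effect in the model". A random class effect may be added if needed.

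The COVID-19 text changes data collection but not the analysis. It adds no term for collection method, no sensitivity analysis and no separate reporting of the first class.

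**The concern.** In the first class, sessions 1 to 3 fall under one procedure and sessions 4 to 10 under another, so collection method is tied to time within the same Veterans. Going over answers privately with a staff member may change how people rate their emotions. If it does, a model containing only time has nowhere else to put the difference.

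mDES positive emotion is one of the outcomes used to judge whether CM shows promise, and the Sample size assessment says the purpose is to obtain effect sizes that guide later studies. At stake is the mDES effect size carried into the planned trial. No confirmatory test depends on it.

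**Working it through.** **Inputs from the plan.** mDES positive emotion: mean change 4.8, SD 9.1, effect size 0.53 (Sample size assessment). CM sample: 24 to 30 in three groups of 8 to 10 (same place); the CM intervention paragraph also allows two groups. Ten sessions, with three held before the switch. Three withdrawals for lack of technology.

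**The plan's own figure.** 4.8/9.1 = 0.527, which reproduces 0.53. So 9.1 is an SD of change. It can convert points into effect-size units, but it is not the spread of weekly scores.

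**Two inferences.** The COVID-19 text does not name the mDES, but it is the only scale the documents describe as weekly. Session 4 as the first virtual session follows from the reference to the previous three sessions.

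**What the model can absorb.** A random class effect adds one constant to all of a class's scores. A step between sessions 3 and 4 varies within the class, so it stays in the time effect.

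**Effect in the first class.** Let the step be c points.
- Last session minus first: the artefact is c.
- Straight line over sessions 1 to 10: slope = Σ(t − 5.5)m / Σ(t − 5.5)², with m = 0 for sessions 1–3 and 1 for sessions 4–10. This is 10.5/82.5 = 0.1273 per session. Over nine intervals it is 9 × 0.1273 = 1.145c.

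**Share reaching the pooled estimate** (first class as a fraction of Veterans contributing):
- Three equal classes: 8/24 = 10/30 = 0.33.
- Three classes, the three withdrawals all from the first: 5/21 = 0.24 to 7/27 = 0.26.
- Two classes of 10, same withdrawals: 7/17 = 0.41.
- Straight line, three equal classes: 1.145 × 0.333 = 0.38. Straight line and two classes together: 1.145 × 7/17 = 0.47.

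The documents do not say which class lost the three Veterans. The first is the only class they describe as under way when the hold began. Two equal classes without those losses would give one half.

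**In points.** The documents give no value for c, so these values are assumptions. Last-minus-first, three classes, shares 5/21 to 1/3:

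| Assumed c | Pooled artefact (points) | Divided by 9.1 | As % of 4.8 |
|---|---|---|---|
| 1 | 0.24 to 0.33 | 0.03 to 0.04 | 5 to 7 |
| 2 | 0.48 to 0.67 | 0.05 to 0.07 | 10 to 14 |
| 3 | 0.71 to 1.00 | 0.08 to 0.11 | 15 to 21 |
| 4.8 | 1.14 to 1.60 | 0.13 to 0.18 | 24 to 33 |

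**Would a method term solve it?** In the first class, method and session number correlate at 10.5/√(82.5 × 2.1) = 0.80, giving a variance inflation of 1/(1 − 0.636) = 2.75 and a standard error √2.75 = 1.66 times as large. Pooled with two all-virtual classes, under a random-intercept model with full attendance, the factor is about 1.13. The term removes the artefact arithmetically. But its coefficient combines method, virtual delivery and the pandemic, because all three arrive together.

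**The case against.** The strongest reply is that no document shows a method effect. Mailed forms that staff review and collect are compatible with self-completion followed by read-back, which might change answers very little. This stands, and the point must stay conditional.

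Several stronger readings are tempting but unsupported:
- A reader might infer that scores also move from after the group to before it. The in-person text says only that the form is completed at the session; completion on arrival would fit.
- A reader might infer that Veterans who miss a session now get a score. The COVID-19 text does not address this.
- A reader might infer that a class running when the hold ends would switch back mid-course. The text speaks only of cohorts enrolled during the hold.
- A reader might infer that the methods can never be separated later. In the first class, session number already identifies them.
- A reader might put the distortion near 39% of the benchmark. That needs a shift of half of 9.1 (an SD of change), only two classes and all three withdrawals from a first class of 10: 0.5 × 9.1 × 7/17 = 1.87, and 1.87/4.8 = 39%. It stacks unfavourable assumptions.

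It is also fair to say that the switch is part of a wider disruption. The first class's post-intervention assessments also move to WebEx, and the pandemic itself may alter mood. That limits what any adjustment can isolate, but it strengthens the case for showing this class separately.

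Finally, the plan disclaims inferential efficacy testing, and its primary outcomes are enrollment and completion. This settles the severity as modest.

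**Conclusion.** The point holds in conditional form. Collection of the weekly questionnaires changes after session 3 of the first CM class, and nothing in the Analytic plan separates that change from time. Any shift it causes would enter that class's mDES change in full (1.0 times the shift for last minus first, 1.15 times for a straight line). About one quarter to one third would reach the pooled estimate with three classes, and about 0.4 with either two classes or a linear trend.

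This rests on the weekly questionnaires including the mDES, the switch falling at session 4, and later classes each using one method throughout. The documents do not support saying that the mDES result is biased, or in which direction. The enrollment and completion outcomes are untouched.

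**What to change.** 1. In Additional final visit measures and the Temporary COVID-19 Updates, state one mDES collection method for all remaining classes, virtual or in person: self-completed before the session, with staff only recording the answers. Have staff log method and date with each score, since participants are told not to write the date on the forms.
2. In the Analytic plan, report mDES change and effect size both with and without the first class. Show that class separately, with sessions 1–3 and 4–10 marked. Do not rely on a method term alone, because it would estimate the combined effect of method, virtual delivery and the pandemic.

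The cost is protocol wording, a method and a date entry per weekly form, and some extra reporting. Later in-person classes would also need a little staff time to record answers before the group. The estimate without the first class is less precise. With three classes its interval is about √(21/16) = 1.15 to √(30/20) = 1.22 times as wide; with two, about √(17/10) = 1.30 times. These ratios assume the same SD and ignore the small change in the t quantile. Because both estimates are shown, no data are discarded.

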Inclusion criteria: (1) VASDHS patient, (2) current age > 55 years, (3) mild-to-moderate anxiety or depressive symptoms (as defined above) at the time of enrollment, (4) stated intention to attend the 10 group sessions at the scheduled times at the VASDHS in addition to the baseline and follow-up study assessment visits, as well as to complete the outside homework assignments, and (5) provides written informed consent for participation.

Exclusion criteria: (1) No active suicidality/homicidality in the preceding six months, (2) untreated alcohol or substance use disorders (those co-enrolled in the VASDHS Alcohol and Drug Treatment Program will be eligible), (3) changes to psychiatric medications within six months of baseline evaluation (changes to medications during the course of the study will be permitted as determined appropriate by Veteran's treating clinicians, but changes will be recorded to further describe the sample), (4) medical and/or psychiatric instability interfering with current ability to engage in the group sessions and outside homework assignments.

As part of the routine clinical service/care, all Veterans referred to the PCMHI service are screened for depressive symptoms with the PHQ-9, and for anxiety symptoms with the GAD-7. Thus we do not expect screen failures among participants who consent the consent process.

Section 10.6 Avoiding coercion of students or employees

10.6) Indicate how coercion of students and/or employees will be avoided:

Students will not be included.

Employees of the investigators will not be recruited, but other VASDHS employees can be recruited /enrolled.

Section 11 - Recruitment

11) Describe, step-by-step, the plans for recruitment of subjects (or selection of subjects as in record review). This description must include how, when, and where potential subjects are approached as well as procedures for identifying potential participants (through medical records, physician referral, third-party sources, etc.). Include how selection is equitable. Indicate if vulnerability to coercion may be present and if so plans to ensure voluntary participation.

Re	cr	mi	tn	no	n	۲	•
IVE	U	ui	CI.	IIIC		L	٠

Potential participants will be recruited through the VASDHS PCMHI program. The investigators will inform the clinical providers of the PCMHI clinics about the study and will provide VASDHS IRB-approved Provider Referral Information sheets, which will assist referring providers in identifying and referring potential participants to the study. Referring PCMHI clinicians who are meeting individually with potential Veteran participants may indicate Veteran interest in participation through a VA-encrypted email or a separate (or addendum to clinical visit) CPRS note using the text template below:

CPRS note: "Veteran is willing to be contacted by phone regarding CBCT study (PI [name]) by the PI or study staff." Provider will add [name] to CPRS note to alert us to its presence.

In addition, PCMHI providers will be given our IRB-approved participant brochure summarizing the project that can be given to appropriate patients to call our study staff for further information about the study.

Screening:

We request a partial HIPAA waiver to conduct pre-screening CPRS chart review for all interested participants to ensure there are no immediate exclusion criteria noted prior to initiating contact with interested participants via phone (see Protocol Section 12).

Individuals who agree to be contacted by phone by the PI or study staff, as well as those who call our study phone number, will be asked to provide verbal consent to participate in a brief telephone screen (see attached Oral Consent/Phone Screen form). If no immediate exclusions are identified via the telephone screen, participants will be scheduled to come in for an in-person study visit (i.e., "Baseline Visit"), to review and discuss the information in the IRB-approved informed consent and HIPAA documents, and to be screened to determine eligibility to participate in the Compassion Meditation sessions

During the Baseline Visit, [name], [name], or [name], or an appropriately trained RA under our supervision will meet with the participant to review and discuss the information in the IRB-approved informed consent and HIPAA documents. Participants will be provided with an opportunity to read the consent document and/or to have it read to them. After thorough discussion, including answering any questions from the potential participant, willing participants will be asked to sign the informed consent and HIPAA documents to indicate their consent to participate.

Equity will be fostered by adherence to the inclusion/exclusion criteria listed above as the basis for enrollment. As part of the informed consent process, potential participants will be informed that participation is entirely voluntary so as to minimize any potential feelings of coercion or undue influence.

Section 11.1 Recruitment Materials

11.1) Identify all recruitment materials (flyers, advertisements, letters, etc.) that will be used; include the web address for any web-based advertisements. The text of all communications with prospective participants must be reviewed and approved by the IRB before it can be used. You will be reminded to attach copies of recruitment materials to the initial submission packet.

Note: Posting of flyers with pull tabs is not permitted within VASDHS (including the VMRF building).

The recruitment materials will include a VASDHS IRB-approved Provider Referral Information sheet, which will be given to PCMHI referring providers only, as well as an IRB-approved participant brochure that may be given to potential Veterans participants. Any additional recruitment materials will be submitted as protocol amendments for IRB review and approval; no recruitment materials will be used unless and until approved by the VASDHS IRB.

Section 12 - Informed Consent

12)	Indicate	whether	or not	each ca	tegory (of consent	is in	volved	in thi	s study:

12a) Will the study team obtain information or biospecimens for the purpose of screening, recruiting, or determining the eligibility of prospective subjects without (or prior to) obtaining informed consent of the prospective subject or the prospective subject's LAR?

⊙ Yes ○ No

Check one or both of the below boxes if they apply to this study:

Overall, risks of harm from this protocol itself appear unlikely and/or are unlikely to result in enduring harm or disability.

Section 15 - Risk Management

15) Describe the procedures for protecting against or minimizing any potential risks/discomforts, and the adequacy of resources for conducting the study and resources participants may need as a consequence of the research. When applicable, include detail of the following safety measures:

(a) The type of safety information to be collected, including AEs;
(b)

Frequency of safety data collection; (c) Frequency or periodicity of review of cumulative safety data;

(d) Statistical tests for analyzing the safety data to determine if harm is occurring; and Conditions that trigger an immediate suspension of the research. See ? for further requirements.

Interviewers are trained to be sensitive and respectful of any concerns that subjects may have, including their right to refuse to answer any questions that make them uncomfortable, and their right to stop the interview, leave a group session, or terminate participation at any time. Study staff are also trained to be alert and offer breaks as appropriate to the participant's needs.

Confidentiality of study materials is protected by using coded ID numbers, rather than names or other personally identifiable information (PII), on hardcopy and electronic study documents and in any analyses. Hard copy data will be maintained in locked file cabinets at the VASDHS and electronic data will be stored in password-protected files in the PI's R Drive folder behind the secure VA firewall. All hardcopy and electronic data will be accessible only to IRB-approved study personnel. The code-book that links ID numbers to participants will be maintained in a locked cabinet accessible on a "need to know" basis to IRB-approved study personnel.

As per standard VA group therapy protocols, during group sessions all participants will be reminded of the importance of keeping information about others in the group confidential, and participants will also be informed of this risk and their right to not reveal private information during the group sessions.

The compassion meditation training as well as the psychoeducational healthy aging groups will be led by experienced clinical psychologists, with VA privileging for provision of psychotherapy and mental health clinical assessments. The group leader will be sensitive and alert for participants whose conditions appear to worsen and referral for appropriate standard clinical care will be made. In addition, no changes to psychotropic treatment will be initiated as part of participation in this study.

Risks involved in phlebotomy are minimized by using only highly experienced, licensed phlebotomists at the VA Clinical Laboratory who will have a fully self-contained phlebotomy kit for each subject. After data extraction, any residual blood from each sample will be destroyed and the extracted data will be subsequently stored in password-protected files in the PI's R Drive folder behind the secure VA firewall.

In addition, Drs. [name], [name], [name], and [name] are VA-approved mental health clinicians, and one or more will be available at all times in person or by phone during study visits to assess and address any emergent clinical concerns that may arise.

Section 17 - Potential Benefits

17) Discuss benefits that may be gained by the subject as well as potential benefits to society in general (see ? for guidance)

Through this project, we will learn more about the feasibility of employing compassion meditation training in future larger scale studies to examine its potential as an effective intervention for psychological distress among older Veterans in primary care. This is important given the under-utilization of mental health services among psychologically distressed, older VA patients. In addition, as a strengths-focused intervention, we may find CM more acceptable to this population than are symptom-focused treatments. We will also learn whether the psychoeducational group focused on healthy aging is a feasible control condition for subsequent use in a randomized clinical trial. Veterans may or may not benefit from participation in either group. Participants in the psychoeducational group may learn useful information relevant to promoting successful aging, such as information about exercise, diet and nutrition, as well as positive mental health factors such as resilience. It is possible that participants in the compassion meditation training group may experience improvement in positive emotions, reduced negative emotions, and better social connectedness.

The feasibility information from this study is of critical importance to guide and inform a subsequent larger-scale VA Merit Award application that will be focused on a hypothesis driven RCT to determine the

effectiveness of compassion meditation training as an intervention for psychological distress among older Veterans. It will provide information about adaptations needed to the specific manualized compassion meditation protocol/manual, CBCT-Vet, and for the psychoeducational healthy aging group, so that both are feasible and appropriate for the future RCT and for use with this study population. This line of research, moreover, can fill an essential unmet need for novel strengths-focused interventions to address anxiety and depressive symptoms among older Veterans in primary care.

Section 18 - Risk/Benefit Analysis

18) Discuss why the risks to subjects are reasonable in relation to the anticipated benefits to subjects and in relation to the importance of the knowledge that may reasonably be expected to result.

Given the potential value for research that may benefit future patients, as well as the possible but uncertain benefit to participants, and the relatively minor associated risks, with adequate provisions for protection against risks, the risks associated with this protocol are reasonable and outweighed by potential benefits.

Section 20 - Compensation for Participation

20) Provide all details and justifications of the compensation plan. See ? for detailed requirements.

Participants will receive payment for participation at 2 time points: \$100 for the first visit and \$150 for the final visit, for a total of \$250 per person. This level of compensation is concordant with that provided in similar psychosocial intervention research and is intended to compensate participants for the time and burden associated with the research procedures and assessments.

Post-Intervention and Participant Withdrawal Data:

Participants who withdrew from the study due to lack of technology (devices and/or WIFI) necessary for virtual training sessions and data collection during the COVID-19 administrative hold will be compensated \$75 for completing the post-intervention questionnaires.

health care use among older veterans in the United States. Psychiatric Services, 66(5), 500-506.

Conner, K. O., Copeland, V. C., Grote, N. K., Koeske, G., Rosen, D., Reynolds, C. F., & Brown, C. (2010). Mental Health Treatment Seeking Among Older Adults With Depression: The Impact of Stigma and Race. The American Journal of Geriatric Psychiatry, 18(6), 531-543.

Geiger, P. J., Boggero, I. A., Brake, C. A., Caldera, C. A., Combs, H. L., Peters, J. R., & Baer, R. A. (2016). Mindfulness-based interventions for older adults: a review of the effects on physical and emotional well-being. Mindfulness, 7(2), 296-307.

Jeste, D. V., [name], B. W., Rettew, D. C., & Boardman, S. (2015). Positive psychiatry: Its time has come. Journal of Clinical Psychiatry, 76, 675-683.

